10.2.2 Double-blind Treatment Period

Eligible subjects who have washed out prohibited medications will be randomized to double-blind study drug.

10.2.2.1 Baseline Visit (Visit 2, Day 1)

The following procedures will be performed on Day 1 in the study clinic:

1. Review inclusion/exclusion criteria.
2. Record responses to DLQI and EQ-5D Quality of Life Questionnaires

3. Perform physical examination.
4. Record vital signs (blood pressure and pulse).
5. Record concomitant medications and concomitant therapies.
6. Record IGA.
7. Record VIIS.
8. Record roughness assessment.
9. Record palm/sole assessment.
10. Record palm/sole assessment of fissuring.
11. Record ectropion score.
12. At sites where the photographic substudy is conducted, take photographs of subjects who have provided informed consent for the photography.
13. Perform a 12-lead ECG.
14. Perform urine pregnancy test for WOCBP.
15. Collect blood and urine for routine laboratory tests (subject must be fasting; i.e., at least 8 hours).
16. Randomize via IWRS.
17. Collect a predose PK blood sample (all subjects).
18. Among subjects who consent to participate in the PK substudy, ensure that PK lines are placed before IP application. The IP will be applied in the clinic at this visit, and samples for PK will be taken at 1, 2, 4, 8, 12, and 24 hours postdose on Day 1.
19. Among subjects in the PK study, perform additional ECGs at times of serial sampling.
20. Clinic staff instructs subject on study drug application, applies initial study drug dose and measures amount used (i.e., study staff will weigh the 50-g tube before and after the first application to determine the fixed dose amount for each subject). If the product will be applied at home by someone other than the study subject, it is recommended that this person assist with application at this visit to learn how the IP is applied.
21. Assess and record local tolerance/AEs.
22. Dispense study drug and diaries.
23. Advise subjects regarding permitted emollient(s) for use on nontreatment days; use of emollient(s) and/or sunscreen on study drug treatment days within 4 hours before or after study drug application is prohibited. Remind subjects that at least 24 hours must have elapsed since IP application before their next visit. Subjects should not to apply IP on visit days until after the visit.

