13. STATISTICS

13.1. Statistical Analysis

This section presents a summary of the planned statistical analyses. A SAP that describes the details of the analyses to be conducted will be written prior to database lock.

Unless otherwise indicated, all testing of statistical significance will be two-sided, and a difference resulting in a P value of ≤ 0.05 will be considered statistically significant.

Summary statistics will be provided for the variables described below. For continuous variables, these statistics will include the number of subjects, mean, standard deviation (SD), median, minimum, and maximum. For categorical variables, these statistics will include the number and percentage of subjects in each category.

The primary analysis period is the first 90 days of treatment (i.e., the Double-blind Period). Overall unblinding will take place at the end of the Double-blind Period of the study only after the database is locked. A second analysis will take place for endpoints assessed from Day 90 through the OLE Period. The baseline for the safety and efficacy parameters will be measured at Visit 1 or Visit 2, per the Schedule of Events for both the Double-blind Period ([Table 2-1](#)) and OLE ([Table 2-2](#)).

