2.2. Schedule of Events

Table 2-1: Schedule of Events for Double-blind Period

	Screening (-35 days to -1 day) Washout up to 3 months ^a	Double-blind Treatment Period						
		Baseline (Day 1)	Telephone Visit (Day 7)	Day 14 ± 5 days	Day 30 ± 7 days	Telephone Visit (Day 45)	Day 60 ± 7 days	Day 90 ^{b,c} ± 7 days (ET)
Visit	1	2		3	4		5	6
Week		1		2	4		8	12
Written informed consent	X							X ^a
Assign screening number	X							
Inclusion/exclusion criteria	X	X						
Demographics	X							
Medical history	X							
Physical examination	X	X ^d						X ^c
Vital signs (blood pressure and pulse)	X	X		X	X		X	X
Height, weight, and BMI	X							X
IGA assessment ^e	X	X		X	X		X	X
VIIS ^f assessment	X	X		X	X		X	X
Roughness assessment ^g	X	X		X	X		X	X
Palm/sole assessment	X	X		X	X		X	X
Palm/sole fissuring assessment ^h	X	X		X	X		X	X
Ectropion score	X	X		X	X		X	X
Photographs ⁱ		X			X			X
Quality of life per Dermatology Life Quality Index (DLQI)		X		X	X		X	X

	Screening (-35 days to -1 day) Washout up to 3 months ^a	Double-blind Treatment Period						
		Baseline (Day 1)	Telephone Visit (Day 7)	Day 14 ± 5 days	Day 30 ± 7 days	Telephone Visit (Day 45)	Day 60 ± 7 days	Day 90 ^{b,c} ± 7 days (ET)
Visit	1	2		3	4		5	6
Week		1		2	4		8	12
EQ-5D Quality of Life Questionnaire		X		X	X		X	X
12-lead ECG ^l	X	X			X			X
Clinical laboratory tests (hematology, chemistry, urinalysis) ^k	X	X			X			X
Serology (hepatitis B surface antigen, hepatitis C)	X							
Pregnancy test for female subjects (serum at Screening; urine subsequently)	X	X			X		X	X
Randomization via IWRS		X						
PK blood sample collection ^l		X		X	X		X	X
Initial study drug application by clinic staff and measurement ^m		X						
Application instructions, advice on emollient and sunscreen use		X	X	X	X	X		
Dispense study drug and diaries ⁿ		X ⁿ		X	X		X	
Concomitant medications	X	X	X	X	X	X	X	X
Tolerability assessment		X		X	X		X	X
Adverse events (and review diaries)		X	X	X	X	X	X	X
Collect all used/unused study drug ^o				X	X		X	X
Provide information about OLE option					X	X	X	

Abbreviations: BMI = body mass index; DLQI = Dermatology Life Quality Index; ECG = electrocardiogram; ET = early termination; HEENT = head, eyes, ears,

nose, throat; ICF = informed consent form; IGA = Investigator's Global Assessment; IWRS = interactive web response system; OLE = open-label extension; PK = pharmacokinetic; WOCBP = women of childbearing potential; VIIS = Visual Index for Ichthyosis Severity

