10.2.1 Screening and Washout

10.2.1.1 Screening Visit (Visit 1)

The subject must complete eligibility screening within 35 days before randomization in the study. The following procedures will be performed during Screening:

1. Obtain written informed consent.
2. Assign a screening number when a subject begins screening.
3. Assess inclusion/exclusion criteria.
4. Collect demographic information.

5. Record medical history, including current therapies (e.g., prescription and nonprescription medications).
6. Perform a physical examination.
7. Measure vital signs (systolic blood pressure [SBP], diastolic blood pressure [DBP], and pulse).
8. Measure height, weight, and calculate body mass index (BMI).
9. Record IGA.
10. Record VIIS.
11. Record roughness assessment.
12. Record palm/sole assessment.
13. Record palm/sole assessment of fissuring.
14. Record ectropion score.
15. Perform a 12-lead ECG.
16. Collect blood and urine for laboratory tests.
17. Perform serum pregnancy test for WOCBP.

Procedures for rescreening subjects who initially fail to meet study entry criteria are described in Section [14.3](#).

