10.2.2.4 Visit 4 (Day 30 ±7 days)

The following procedures will be performed on Day 30 in the study clinic:

1. Record responses to DLQI and EQ-5D Quality of Life Questionnaires.

2. Record concomitant medications and concomitant therapies.
3. Record vital signs (blood pressure and pulse).
4. Record IGA.
5. Record VIIS.
6. Record roughness assessment.
7. Record palm/sole assessment.
8. Record palm/sole assessment of fissuring
9. Record ectropion score.
10. At sites where the optional photographic substudy is conducted, take photographs of subjects who have provided informed consent for the substudy.
11. Assess local tolerance.
12. Record AEs and review diary.
16. Perform a 12-lead ECG
17. Perform a urine pregnancy test for WOCBP.
18. Collect blood and urine for routine laboratory tests (subject must be fasting at least 8 hours).
19. Collect a PK blood sample (all subjects).
20. Among subjects who consent to participate in the PK substudy, ensure that PK lines are placed before IP application. The IP will be applied in the clinic at this visit, and samples will be taken predose and at 1, 2, 4, 8, 12, and 24 hours postdose.
21. Among subjects in the PK study, perform an additional ECGs at times of serial sampling.
22. Collect returned study drug tubes; confirm study drug compliance by weighing returned tube contents and reviewing diaries.
23. Instruct subject on study drug application, and advise subjects regarding permitted emollient(s) and/or sunscreen for use on nontreatment days; use of emollient(s) on study drug treatment days within 4 hours before and after study drug application is prohibited. Remind subjects that 24 hours must have elapsed since IP application before the subject's next visit. Subjects should not apply IP on visit days until after the visit.
24. Weigh new study drug tubes and dispense enough additional study drug until next visit, and new diary.
25. Provide information about OLE option to study subject.

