10.2.4.7 Follow-up Evaluation – Open-Label Extension (Week 26/Visit 11)

At 14 days after the last administration of the IP, the following procedures will be performed:

1. Perform a physical examination.
2. Record vital signs (blood pressure and pulse).
3. Record any concomitant medications/therapies.
4. Record IGA.
5. Record VIIS.
6. Assess roughness.
7. Record palm/sole assessment.
8. Record palm/sole assessment of fissuring.
9. Record ectropion score.
10. Assess and record AEs occurring since the last evaluation and review diary.
11. Perform a urine pregnancy test for WOCBP.

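### On Day 1 the only local tolerability score is listed after the first application and Screening has none, so an untreated score by body area is possible but not assured, mainly for pruritus and erythema

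*Protocol*

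**What the plan says.** The document contains several protocol versions. The most recent one is shown without its Section 10, so the latest visit procedures in hand are those of Amendment 2.

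- **Screening (10.2.1.1).** The list opens with "The following procedures will be performed during Screening" and has 17 items. None is a local tolerability assessment.
- **Baseline, Day 1 (10.2.2.1).** Item 20 is "Clinic staff instructs subject on study drug application, applies initial study drug dose and measures amount used". Item 21 is "Assess and record local tolerance/AEs". No other item on the list concerns tolerance.
- **Table 2-1 (Section 2.2).** The row "Tolerability assessment" is blank at Screening and first marked at Baseline. The mark has no footnote on timing relative to the dose.
- **Section 13.1.** "The baseline for the safety and efficacy parameters will be measured at Visit 1 or Visit 2, per the Schedule of Events". For tolerability that leaves Visit 2 only.
- **Text pointing the other way.** The Synopsis, Sections 7.1 and 9.2, and footnote m of Table 2-1 all have staff apply the first dose once baseline measurements are done. None of them says that tolerability is one of those measurements.

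**The concern.** Local tolerability consists of stinging/burning, pruritus and erythema, scored 0 to 3 in up to five treated areas. Section 5.1 names pruritus as a feature of the disease. Section 10.3 expects that the retinoid may increase erythema and for that reason assigns erythema to local tolerability. An earlier protocol version, cited here only as disease background, describes erythema as present in ichthyosis of every genetic cause. Scores above 0 before any treatment are therefore plausible for these two signs.

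A site that follows the list in order would record a value taken after the first application and carry it as Baseline. Two things would suffer:

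- **The within-subject reference.** Under 11.1.6 an event is treatment-emergent if it starts or worsens after the first application. Application site reactions are recorded as adverse events (11.2.1) and are of special interest (11.3.1). Telling a new or worsened sign from existing disease in a given area is harder without a score from before exposure, and that score cannot be obtained later.
- **The Baseline row of the by-visit summaries (13.1.6.1).** It would show a post-application value under a label that readers take to mean untreated.

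**Working it through.** The plan states no figure to reproduce. The check is a comparison of the texts and a count.

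**1. Order on Day 1 (10.2.2.1).** The other safety baselines come before item 20: physical examination (item 3), vital signs (4), ECG (13) and laboratory tests (15). So do the efficacy scores (6 to 11). Tolerance (21) is the only safety or efficacy baseline listed after the application.

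**2. Is the list order meant as a sequence?** The Amendment 2 change table says that the assessments in this section were rearranged to follow the order in which they are performed. Against that, items 18 and 19 (PK samples and ECGs after dosing) stand before item 20, so the list is not strictly chronological. Those two items state their own timing and item 17 is labelled predose. Item 21 has no label, so nothing moves it from its listed position.

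**3. Comparison with Day 30 (10.2.2.4).** "Assess local tolerance" is item 11, and in-clinic dosing is item 20: "The IP will be applied in the clinic at this visit, and samples will be taken predose". Tolerance comes first here, but item 20 applies only to PK-substudy subjects, so the contrast is limited to them.

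**4. Can another assessment supply the untreated score?**

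- Double-blind marks in Table 2-1: Baseline and Days 14, 30, 60, 90 = 5.
- Extension marks in Table 2-2: Days 104, 120, 150, 180 = 4.
- Total: 5 + 4 = 9. After Day 1: 9 − 1 = 8, all within the treatment periods.
- The follow-up visit has no tolerability mark. Its list (10.2.4.7) contains "Assess and record AEs occurring since the last evaluation and review diary" but no tolerance score.

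Only the Day 1 assessment can be untreated. In the listed order, 0 of 9 are.

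**5. Does anything at Screening stand in for it?** Exclusion criterion 2 (8.2.2) covers current moderate or severe stinging/burning. That is 1 of the 3 signs, and it is not recorded by area.

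**6. Count of scores without an assured untreated value.**

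- Scores per assessment: 3 signs × 5 areas = 15.
- Pruritus and erythema: 2 signs × 5 areas = 10 per subject.
- Planned 120 subjects: 10 × 120 = 1,200 cells.

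These are upper bounds, because only treated areas are scored.

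**The case against.** The strongest reply is that the protocol already implies a predose score. Table 2-1 marks tolerability in the Baseline column, Section 13.1 takes safety baselines from that schedule, and four places put the first dose after the baseline measurements. Read together, tolerability would be one of those measurements. Items 18 and 19 show that list position is weak evidence of sequence. This stands to the extent that a site may properly score before dosing. It does not settle the matter: none of those places names tolerability, and the one numbered instruction puts it after the dose.

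Second, the most recent version's Section 10 is not shown. That stands too. The point is about Amendment 2 and reaches a later version only if its list keeps the same order.

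Several stronger readings are tempting, and the documents do not support them:

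- *That the dose-adjustment or stopping rules fail.* Sections 9.4 and 9.4.1 act on absolute scores and need no reference value.
- *That treatment-emergent status cannot be determined.* Section 11.2 treats conditions present at screening as baseline, 11.2.3 records events arising during Screening, and medical history is taken at Visit 1. None of these is a score by area, but they inform the judgement.
- *That the safety comparison is biased.* The randomized vehicle arm is scored on the same schedule, and the planned tolerability analysis is descriptive, by period, group and visit.
- *That 1,200 scores are lost or wrong.* That figure counts cells. The documents do not say how many would be above 0, or how far a score after one application would differ from an untreated one.

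**Conclusion.** The point holds as a minor design weakness. The Amendment 2 visit list places the only Day 1 tolerability score directly after the first application, Screening has none, and the general statements about baseline measurements do not name tolerability. The texts conflict or leave the timing open, so an untreated score by body area is possible but not assured, chiefly for pruritus and erythema.

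What is weakened is the within-subject judgement of application site reactions and the meaning of the Baseline row in the tolerability summaries. The group comparison with vehicle, the rules in 9.4 and 9.4.1, and the power of the trial are not affected. The size can be stated only as a count, up to 10 scores per subject; no effect size follows from it.

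The conclusion assumes that some sites would follow the numbered order, and it covers a later version only if that version's Day 1 list is unchanged.

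**What to change.** In 10.2.2.1, add an item before item 20: score stinging/burning, pruritus and erythema on the 0 to 3 scale in each area to be treated (chest/abdomen, back, arms, legs, face/neck). Keep item 21 as the check for reactions and adverse events after application. In Table 2-1, footnote the Baseline tolerability mark to say that this score is taken before the first application. Make the same edit in any later version whose Day 1 list keeps the present order.

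The cost is a few minutes at one visit and one footnote. Dosing, eligibility, sample size and the rules in 9.4 and 9.4.1 do not change. Where sites already score before dosing, the edit only records what they do.

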10.2.2.2 Telephone Visit (Day 7)

Clinic staff will telephone subject to assess safety and to record concomitant medications/therapies. Staff will instruct subject on study drug application, advise subjects regarding permitted emollient(s) for use on nontreatment days (use of emollient(s) and/or sunscreen on study drug treatment days within 4 hours before or after study drug application is prohibited), and remind subjects that at least 24 hours must have elapsed since IP application before their next visit. Subjects should not apply IP on visit days until after the visit. An unscheduled clinic visit may be performed, if necessary.

10.2.2.3 Visit 3 (Day 14 ±5 days)

The following procedures will be performed on Day 14 in the study clinic:

1. Record responses to DLQI and EQ-5D Quality of Life Questionnaires.
2. Record concomitant medications and concomitant therapies.
3. Record vital signs (blood pressure and pulse).
4. Record IGA.
5. Record VIISIGA.
6. Record roughness assessment.
7. Record palm/sole assessment.
8. Record palm/sole assessment of fissuring
9. Record ectropion score.
10. Assess local tolerance.
11. Record AEs and review diary.
12. Collect a PK blood sample (all subjects).
13. Collect returned study drug tubes; confirm study drug compliance by weighing returned tube contents and reviewing diaries.
14. Instruct subject on study drug application, and advise subjects regarding permitted emollient(s) and/or sunscreen for use on nontreatment days; use of emollient(s) on study drug treatment days within 4 hours before or after study drug application is prohibited. Remind subjects that 24 hours must have elapsed since IP application before the subject's next visit. Subjects should not apply IP on visit days until after the visit.
15. Weigh new study drug tubes and dispense enough additional study drug until next visit, and new diary.

10.2.2.4 Visit 4 (Day 30 ±7 days)

The following procedures will be performed on Day 30 in the study clinic:

1. Record responses to DLQI and EQ-5D Quality of Life Questionnaires.

2. Record concomitant medications and concomitant therapies.
3. Record vital signs (blood pressure and pulse).
4. Record IGA.
5. Record VIIS.
6. Record roughness assessment.
7. Record palm/sole assessment.
8. Record palm/sole assessment of fissuring
9. Record ectropion score.
10. At sites where the optional photographic substudy is conducted, take photographs of subjects who have provided informed consent for the substudy.
11. Assess local tolerance.
12. Record AEs and review diary.
16. Perform a 12-lead ECG
17. Perform a urine pregnancy test for WOCBP.
18. Collect blood and urine for routine laboratory tests (subject must be fasting at least 8 hours).
19. Collect a PK blood sample (all subjects).
20. Among subjects who consent to participate in the PK substudy, ensure that PK lines are placed before IP application. The IP will be applied in the clinic at this visit, and samples will be taken predose and at 1, 2, 4, 8, 12, and 24 hours postdose.
21. Among subjects in the PK study, perform an additional ECGs at times of serial sampling.
22. Collect returned study drug tubes; confirm study drug compliance by weighing returned tube contents and reviewing diaries.
23. Instruct subject on study drug application, and advise subjects regarding permitted emollient(s) and/or sunscreen for use on nontreatment days; use of emollient(s) on study drug treatment days within 4 hours before and after study drug application is prohibited. Remind subjects that 24 hours must have elapsed since IP application before the subject's next visit. Subjects should not apply IP on visit days until after the visit.
24. Weigh new study drug tubes and dispense enough additional study drug until next visit, and new diary.
25. Provide information about OLE option to study subject.

10.2.2.5 Telephone Visit (Day 45)

Clinic staff will telephone subject to assess safety and to record concomitant medications/therapies. Staff will instruct subject on study drug application, advise subjects regarding permitted emollient(s) and/or sunscreen for use on nontreatment days (use of emollient(s) on study drug treatment days within 4 hours before or after study drug application is prohibited), and remind subjects that 24 hours must have elapsed since IP application before the subject's next visit. Subjects should not to apply IP on visit days until after the visit. An unscheduled clinic visit may be performed, if necessary. Staff will remind subject about OLE option.

10.2.2.6 Visit 5 (Day 60 ±7 days)

1. Record responses to DLQI and EQ-5D Quality of Life Questionnaires.
2. Record concomitant medications and concomitant therapies.
3. Record vital signs (blood pressure and pulse).
4. Perform a urine pregnancy test for WOCBP.
5. Record IGA.
6. Record VIIS.
7. Record roughness assessment.
8. Record palm/sole assessment.
9. Record palm/sole assessment of fissuring
10. Record ectropion score.
11. Assess local tolerance.
12. Record AEs and review diary.
13. Collect a PK blood sample (all subjects).
14. Collect returned study drug tubes; confirm study drug compliance by weighing returned tube contents and reviewing diaries.
15. Weigh new study drug tubes and dispense enough additional study drug until next visit, and new diary.
16. Instruct subject on study drug application, and advise subjects regarding permitted emollient(s) and/or sunscreen for use on nontreatment days; use of emollient(s) and/or sunscreen on study drug treatment days within 4 hours before and after study drug application is prohibited. Remind subjects that 24 hours must have elapsed since IP application before the subject's next visit. Subjects should not apply IP on visit days until after the visit.
17. Provide information about OLE option.

10.2.2.7 Visit 6 (90 ±7 days) or Early Termination

The following procedures will be performed on Day 90 in the study clinic:

1. Record responses to DLQI and EQ-5D Quality of Life Questionnaires.
2. Perform a physical examination.
3. Record vital signs (blood pressure and pulse).
4. Record concomitant medications and concomitant therapies.
5. Record IGA.
6. Record VIIS.
7. Record roughness assessment.
8. Record palm/sole assessment.
9. Record palm/sole assessment of fissuring.
10. Record ectropion score.
11. At sites where the optional photographic substudy is conducted, take photographs of subjects who have provided informed consent for the substudy.
12. Assess local tolerance.
13. Record AEs and review diary.
14. Perform a 12-lead ECG.
15. Perform a urine pregnancy test for WOCBP.
16. Collect blood and urine for routine laboratory tests (subject must be fasting at least 8 hours).
17. Collect a PK blood sample (all subjects).
18. Collect returned study drug tubes; confirm study drug compliance by weighing returned tube contents and reviewing diaries.

For subjects who successfully complete (i.e., have reliable visit attendance and compliance with IP application, in the investigator's opinion) the initial 12 weeks of double-blind treatment and choose to continue into the OLE, this visit will be the first visit of that portion of the study. All efficacy assessments, safety/tolerability assessments, including clinical laboratory testing, PK from Day 90/Week 12 will be carried over to the OLE and will not be repeated. Subjects will have up to 7 days to decide to enter the OLE; if the subject chooses to continue into OLE, the following additional procedures will be done:

1. Have the subject sign OLE-specific informed consent.
2. Measure subject's weight.
3. Instruct subject on study drug application, and advise subjects regarding permitted emollient(s) and/or sunscreen for use on nontreatment days; use of emollient(s) on study drug treatment days within 4 hours before or after study drug application is prohibited. Remind subjects that at least 24 hours must have elapsed since IP application before the

PK draws at the Week 16 and Week 24 Visits, and not to apply IP on visit days until after the visits.

4. Weigh new study drug tubes and dispense enough additional study drug until next visit (only for subjects who choose to continue into the OLE).
5. Dispense study diary.

10.2.3 Follow-up Telephone Call (± 14 days after Day 90) – Only Subjects Who Do Not Continue into Open-label Extension

Clinic staff will telephone subjects who choose not to continue into the Open-label Extension within 14 days after Day 90 to assess any ongoing AEs.

